6.1.3 Follow Up Period and Trial Completion

The different visits and trial periods are as displayed below in Figure 6.1.3: 1.

R, Randomization visit; EOT, End Of Treatment visit; REP, Residual Effect period; EoR, End Of Residual Effect Period visit; FU, Follow-Up period; EoFU, End of Follow-Up visit

Figure 6.1.3: 1: Visits and trial periods

6.1.3.1 End of treatment visit (EOT)

The EOT visit will be performed after permanent discontinuation of trial medication (either BI 836845, or enzalutamide, whichever is the last drug to be taken) for any reason. The EOT assessment will then be performed as soon as possible (within 7 days), instead of the next planned visit.

Doc. No.: c02304008-15

Page 87 of 241

Proprietary confidential information. © 2022 Boehringer Ingelheim International GmbH or one or more of its affiliated companies. All rights reserved.

6.1.3.2 Residual effect period (REP)

The REP starts immediately after permanent discontinuation of trial medication and ends after 42 days. In this study, the End of Residual Effect Period visit (EoR) is combined with the scheduled FU visit. All AEs collected during this period will also be considered as 'on treatment'.

6.1.3.3 Follow-up period

The follow-up period starts immediately after permanent discontinuation of trial medication. All patients should have at least one follow-up visit 42 days (+7) after permanent discontinuation of trial medication which coincides with the EoR visit.

Additional follow-up visits should be performed in phases Ib and II (until approval of protocol version 10) for patients who withdrew for reasons other than progressive disease or start of further anti-cancer treatment; the additional visits will follow the usual tumour scan assessment schedule as per the Flow Chart, i.e. every 12 weeks from the start of trial.

Prior to approval of protocol version 10, follow-up period for every patient will end at the earliest of the following events

- Lost to follow-up
- Disease progression
- Start of a new anti-cancer therapy
- Death

After approval of protocol version 10, the follow up period for every patient will end after the first follow up visit.

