- 2. EOT: end of treatment visit; within 7 calendar days after permanent termination of trial drug(s). If permanent discontinuation of study drug falls on a scheduled visit, examinations as defined for EOT should be performed instead of the examinations of the scheduled visit
- 3. FU: Follow-up visit; 42 days (+7) after permanent discontinuation of trial medication.

 Additional FU: Patients who have not progressed and not started further anti-cancer therapy at first FU should have additional follow-up visits at scheduled tumour assessments until progression /start of further anti-cancer therapy. Only tumour assessments, AEs and concomitant medication to be reviewed, no other assessments required.
- 4. OP: Observational phase; every 90 days (±15) after last FU, patients will be followed for survival every three months until patient death. Survival information can be obtained via phone contact
- 5. Written informed consent must be obtained before any trial specific screening assessments are performed

- 8. Physical exam: includes a thorough cardiopulmonary, abdominal and lymph node exam and an assessment of the mental and neurological status.
- 9. Vital signs: includes respiration rate respiration rate (after two minutes supine rest), pulse, temperature, and blood pressure. On dosing days, at any time before drug administration.
- 10. 12-lead ECG: 12-Lead resting digital electrocardiogram (ECG) are recorded digitally and in triplicate. ECGs will be performed at: Screening, Cycle 1 on Day 1, Day 8 and Day 15; Cycle 2 on Day 8 and Day 15; Cycle 3 on Day 1, Day 8 and Day 15. Day 1 of Cycles 6, 9, 12 and every 12 weeks thereafter; also EOT and first FUP. See Appendix 10.6 for schedule. ECGs to be taken: Pre-dose (-20 min. to -5 min. before administration of BI 836845 and/or enzalutamide) and immediately after the end of infusion of BI 836845 (up to 15 minutes after end of infusion), or one hour after the administration of enzalutamide. ECGs to be taken prior to PK sample time-points where applicable.
- 12. Safety labs: haematology, coagulation, biochemistry, electrolytes, urinalysis by dipstick before dosing. See section 5.2.5 for details.
- 13. Fasting glucose and HbA1C only at screening and Day 1 of each cycle and EOT.

5.1.2.3 and Appendix 10.6 for schedule.

17. PSA blood sampling at screening, C1D1 and from C3 D1 and at Day 1 of every cycle thereafter.

Boehringer Ingelheim BI Trial No.: 1280.8 Doc. No.: c02304008-15

06 Jun 2022

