Trial Protocol Version 12 Page 13 of 241

Proprietary confidential information. © 2022 Boehringer Ingelheim International GmbH or one or more of its affiliated companies. All rights reserved.

20. Tumour assessment: CT or MRI imaging of the chest, abdomen and pelvis at screening and prior to start C3D1 onwards (see below) according to modified RECIST criteria (version 1.1). If clinically indicated, imaging of any other known or suspected sites of disease using an appropriate method (CT scan or MRI) should be performed. After study entry, all lesions identified during the screening should be followed up at all specified imaging time points. The same radiographic procedure must be used throughout the study. See section 5.1.2.1

A bone scan should be performed at screening, prior to the start C3D1and onwards according to schedule below.

Tumour assessment and bone scans will be performed at the following time points until progression/start of further anti-cancer therapy (assessments may be performed up to 7 days prior to the scheduled assessment date):

- At screening: all patients will have a CT or MRI and bone scan at screening, unless valid results are available from a scan performed within 28 days prior to start of study treatment, as part of routine clinical practice
- Week 8 (49-56 days after randomisation)
- Week 16 (105-112 days after randomisation)
- Week 24 (161-168 days after randomisation)
- Every 12 weeks thereafter (i.e., during week 35-36 (245-252 days after randomisation), during week 47-48 (329-336 days after randomisation), etc...)

In the event of an interruption/delay to treatment the tumour assessment schedule should not be changed.

- 21. All patients should have a tumour assessment/bone scan at EOT visit regardless of the reason for discontinuation, unless the last evaluation was performed within 4 weeks of EOT.
- 22. Optional physical examination.
- 23. If not recovered at EOT, or new AE, or drug related death.
- 24. Dispensing of enzalutamide at every weekly visit. However for patients in Arm B and those patients in Arm A which discontinue BI 836845 permanently, from cycle 4 onwards, enzalutamide will be dispensed only on Day 1 of each cycle, e.g. C4D1, C5D1 onwards.
- 25. For more details on patient completion, see section 6.1.3.5

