Assessments will be performed at screening, or if valid results are available as part of routine clinical practice and are within 28 days prior to start of study treatment, repeat imaging will not be required. Imaging will be at baseline and then every 2 cycles (8 weeks) up to week 24 and then every 3 cycles (12 weeks) thereafter i.e. prior to the start of cycles 3, 5, 7, 10 onwards. Tumour assessments may be performed up to 7 days prior to the scheduled date for start of the relevant cycle/assessment date.

In the event of a delay, interruption or discontinuation of treatment, tumour assessment should continue to follow the original schedule. The schedule should be followed until progression is observed or until the patient commences further treatment for disease, whichever occurs first. For patients who prematurely discontinue study medication without disease progression, tumour assessments should continue to be performed until disease progression or start of further treatment.

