Trial Protocol Version 12 Proprietary confidential information. © 2022 Boehringer Ingelheim International GmbH or one or more of its affiliated companies. All rights reserved.

Patient status	To be collected at every follow-up visit. Information collected on last contact date, start of new anticancer therapy, or death.
Patient completion	Performed as per section 6.1.3.5

Additional follow-up visits:

Until approval of protocol version 10, subsequent follow-up visits will be required where a patient has withdrawn from the study treatment for reasons other than disease progression, or start of further anti-cancer therapy, or death, will continue with follow-up visits at scheduled tumour assessments until one of the above mentioned criteria have been met. Only AE and concomitant medication information will be collected at these visits.

Observation Visits:

Until approval of protocol version 10, patients that have withdrawn from the study participation due to disease progression, or start of other anti-cancer therapy, they will enter an observation period and be contacted every 90 days (3 months).

Patient status	Information collected on last contact date, start of new anti-cancer therapy, or death.
Patient completion	Performed as per section 6.1.3.5

Proprietary confidential information. © 2022 Boehringer Ingelheim International GmbH or one or more of its affiliated companies. All rights reserved.

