5.1.3 Phase II

The primary endpoint for the phase II part of the study is PFS based on investigator assessment.

PFS is defined as the time from randomisation until radiological tumour progression in bone (based on PCWG2 criteria) or soft tissue (based on modified RECIST 1.1) or death from any cause, whichever occurs earlier.

Tumour assessments will be performed at screening, week 8, week 16, week 24 and then every 12 weeks thereafter (more details in CTP Flow Chart).

For each follow-up (FU) imaging time-point an overall tumour response will be determined for soft tissue according to modified RECIST 1.1 (R09-0262 and Appendix 10.4 of the CTP) and for bone according to the prostate cancer clinical trials working group (PCWG2) criteria (R13-1642). The overall tumour response for each imaging time-point according to modified RECIST 1.1 will be selected from the following categories: Complete Response (CR); Partial Response (PR); Stable Disease (SD); No disease (ND); Progressive Disease (PD); Non-CR/Non-PD; Not Evaluable (NE). The overall tumour response for each imaging time-point (if clinically indicated) for bone lesion will be selected from the following categories: Non-progressive disease (Non-PD); Progressive disease (PD); Not Evaluable (NE).

Some patients enter the trial without any target or non-target lesion according to RECIST 1.1. Until new lesions appear and a progression is reported for this patient, the response assessment for such patients will be set to No Disease (ND) (see also Section 5.4.7).

For details on the imaging process and RECIST evaluation, see Section 5.1.2 and Section 10.4 of the CTP.

Derivation of endpoint PFS

Derivations below are described in days. However, the endpoints below will be presented in months in the outputs produced for the Clinical Trial Report (CTR).

For patients with 'event' as an outcome for PFS: (according to modified RECIST version 1.1 or PCWG2)

• PFS [days] = date of outcome - date of randomisation + 1.

For patients with 'censored' as an outcome for PFS: (according to modified RECIST version 1.1 or PCWG2)

• PFS (censored) [days] = date of outcome - date of randomisation + 1.

The censoring rules for PFS (i.e. outcome and date of outcome) are given in Table 5.1.3: 1. Clinical disease progression will not be considered for determination of a PFS event, unless the outcome of the progression is death.

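### Protocol 6.1.3.3 and 6.2.3 conflict with 5.1.2.1 and the flow chart on scans after phase II patients stop treatment without progression, so primary-endpoint progressions may be misdated or, if scans are omitted, missed

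*Protocol*

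**What the plan says.** SAP 5.1.3: "The primary endpoint for the phase II part of the study is PFS based on investigator assessment". Its time origin is randomisation.

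Protocol 5.1.2.1 sets imaging "every 2 cycles (8 weeks) up to week 24 and then every 3 cycles (12 weeks) thereafter" and covers patients who stop: "In the event of a delay, interruption or discontinuation of treatment, tumour assessment should continue to follow the original schedule". Footnote 20 of the phase II flow chart in force until version 10 gives the same time points in days from randomisation; week 16, for instance, is days 105-112. Footnote 3 of that chart describes the additional follow-up visits: "Only tumour assessments, AEs and concomitant medication to be reviewed, no other assessments required".

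Two other places differ:

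- Section 6.1.3.3 sends the additional visits to the usual Flow Chart scan schedule, but explains it as "i.e. every 12 weeks from the start of trial".
- Section 6.2.3 says these patients "will continue with follow-up visits at scheduled tumour assessments until one of the above mentioned criteria have been met", and then: "Only AE and concomitant medication information will be collected at these visits".

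The grids also differ. The phase Ib chart has an additional follow-up column with a scan entry. The phase II chart has no such column and no scan entry under follow-up, although PFS is the primary endpoint only in phase II.

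**The concern.** The expected control median PFS is about 3 months (Protocol 7.6), so much of the event information falls in the first 24 weeks. That is the only period in which an 8-weekly and a 12-weekly schedule disagree. A patient who stops early for a reason other than progression depends on follow-up scans for a correctly dated event. One section gives a site the wrong interval for those scans, and another leaves them out of the data to be collected.

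Two things are at stake. Progression dates may shift relative to patients still on treatment, and progressions may never be imaged. The trial is open-label, with weekly infusions in one arm only. If stopping without progression differs by arm, either error could bias the hazard ratio.

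**Working it through.** **1. The texts side by side (phase II, off treatment, not progressed, before version 10)**

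| Place | Timing | Scans included? |
|---|---|---|
| 5.1.2.1 | weeks 8, 16, 24, then 12-weekly | yes |
| Flow-chart footnotes 3 and 20 | same, from randomisation | yes |
| 6.1.3.3 | refers to Flow Chart, glossed as 12-weekly from trial start | implied |
| 6.2.3, follow-up visits table | not given | yes, if applicable |
| 6.2.3, additional visits | at scheduled tumour assessments | not listed |
| Phase II grid | none | no entry |

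This gives two scan timings, plus a separate conflict over what is collected. From week 24 onward the timings agree.

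**2. The plan's own figures**

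Table 7.6:2 takes the log hazard ratio as normal with variance 4/events. At 60 events and a true HR of 0.65, P(HR ≤ 0.8) = Φ[(ln 0.8 − ln 0.65)/√(4/60)] = Φ(0.2076/0.2582) = 0.789. At a true HR of 0.70 it is 0.697, and at 1.0 it is 0.194. The table gives 0.79, 0.70 and 0.19.

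For Table 7.6:3, solve 80(1 − c)F(T, A) = 60, where c is the permanently censored share, A the accrual period and F the event fraction formula in 7.6. With c = 20%, A = 12 months and medians of 3 and 4.6 months, T = 22.5 months, as printed. The other seven durations also reproduce.

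**3. Dating under the 12-weekly gloss**

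For a patient off treatment before week 8, compare the next scan on {8, 16, 24} with the next on {12, 24}. Assume exponential progression times, as in 7.6, and ignore the EOT scan.

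| True progression (weeks) | 5.1.2.1 date | 6.1.3.3 date | Shift (weeks) | Share, median 3 months | Share, median 4.6 months |
|---|---|---|---|---|---|
| 0-8 | 8 | 12 | +4 | 0.481 | 0.429 |
| 8-12 | 16 | 12 | −4 | 0.174 | 0.174 |
| 12-16 | 16 | 24 | +8 | 0.140 | 0.151 |
| 16-24 | 24 | 24 | 0 | 0.205 | 0.246 |

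Shares are among progressions by week 24.

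- Median 3 months: 4(0.481) − 4(0.174) + 8(0.140) = +2.35 weeks.
- Median 4.6 months: 4(0.429) − 4(0.174) + 8(0.151) = +2.23 weeks.
- Median 4.3 months: +2.25 weeks.

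**4. Does the gloss lose events?**

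SAP 6.7.2 assigns days 1-85 to week 8, 86-141 to week 16 and 142-211 to week 24. A week-12 scan is due on day 12 × 7 + 1 = 85. Done up to 7 days early (days 78-85), it fills the week-8 window. A week-24 scan (days 162-169) fills its own window. Only the week-16 window is empty. Under SAP Table 5.1.3:1, progression after one missed assessment is still an event. If the week-24 scan were missed as well, there would be two consecutive gaps and the patient would be censored.

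**5. The no-scan reading of 6.2.3**

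An EOT scan at week 5, say, falls in the week-8 window. With nothing afterwards, progression is never imaged. Once the week-16 and week-24 windows have passed empty, a later death is censored at the EOT scan.

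The documents do not say how many patients this would affect, so the censoring rates above 20% below are assumptions. At 23 months, with A = 12 and medians of 3 and 4.6 months, F = 0.943:

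| Permanently censored | Events | P(HR ≤ 0.8), true HR 0.65 | P(HR ≤ 0.8), true HR 1.0 |
|---|---|---|---|
| 20% (plan) | 60.3 | 0.790 | 0.193 |
| 25% | 56.6 | 0.783 | 0.201 |
| 30% | 52.8 | 0.775 | 0.209 |
| 40% | 45.2 | 0.758 | 0.226 |

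These probabilities reflect lost precision only. They do not measure bias from censoring that differs by arm.

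**The case against.** The case for leaving this alone is fairly strong. The operative instruction in 6.1.3.3 is to follow the Flow Chart, so the 12-week phrase is a wrong explanation of a correct cross-reference. Section 6.2.3 keeps its visits at the scheduled tumour assessments until, among other criteria, progression, which presupposes imaging. Its own table of follow-up procedures lists scans. Section 5.1.2.1 is explicit for patients who stop without progression, and the SAP's protocol-violation list cites that section for imaging. The follow-up column of the phase II chart carries footnote 3, which covers the missing entry. An EOT scan is required unless one was done within 4 weeks. Finally, both passages applied only until version 10; the current text is version 12, and phase II results are already available.

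Most of this stands. It makes the 5.1.2.1 schedule the more likely reading and limits the practical effect. It does not remove the contradiction. The last sentence of 6.2.3 and footnote 3 describe the same visits and differ on whether scans belong to them. The follow-up table in 6.2.3 lists scans only where applicable. The EOT scan detects nothing that happens after it. The Flow Chart grid to which 6.1.3.3 refers shows no follow-up scan for phase II.

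**Conclusion.** The inconsistency is real and bears on the primary endpoint. Its effect is conditional on which text a site followed.

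- **6.1.3.3 followed literally:** progressions before week 24 in early stoppers are misdated in both directions. The mean is about +2.2 to +2.4 weeks, an upper bound because it takes every patient as off treatment before week 8 and ignores the EOT scan. No event is lost by this alone.
- **6.2.3 followed literally:** progressions after the EOT scan are not imaged, and some deaths are censored.

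The number of early stoppers, and their split by arm, is not given. The effect on the hazard ratio is therefore unknown.

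A reader might infer three stronger things that the documents do not support:

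- That there are three scan schedules. The third text differs on content and keeps the scheduled timing.
- That progressions are in fact dated late or lost. Some would be dated earlier, and loss requires the no-scan reading.
- That the delay is about 61% of the control median. That figure divides the largest single shift (56 days, or 1.84 months) by the 3-month median. It describes one patient's worst case and does not estimate any change in the median or the hazard ratio.

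**What to change.** - **6.1.3.3:** replace the 12-week explanation with weeks 8, 16, 24 and every 12 weeks thereafter, from randomisation (phase II) or start of treatment (phase Ib).
- **6.2.3:** amend the closing sentence on additional follow-up visits so that the items collected are tumour assessments/bone scans, AEs and concomitant medication.
- **Phase II flow chart in force until version 10:** add an additional follow-up entry for tumour assessment/bone scans, matching the phase Ib chart.

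The cost is protocol wording and one chart entry, with no scan beyond those 5.1.2.1 already requires. Because additional follow-up ended with version 10, the correction mainly sets the record straight. The size of the effect can be settled from data already held: tabulate by arm, for patients who stopped without progression, which scheduled scans were done and which were missed, and report this alongside PFS.

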6.1.3.4 Observation period

Until approval of protocol version 10, all patients in the phase II randomised trial will be followed-up for overall survival every 90 days after the last follow-up visit (as specified in Section 6.1.3.3) until death, lost to follow-up or completion of the whole trial (as specified in Section 6.1.3.6) whatever occurs earlier. For patients who progressed on treatment, this period starts after the first follow up visit. For patients who have not progressed on treatment, this period starts after the last FU visit.

These visits may also be performed by telephone interview in case the patient is unable to visit the investigator.

The following information will be collected during the observation period:

- Date and method of contact
- Further treatment : regimen and drugs name, start and stop dates, reason for stopping this treatment
- Outcome death (date of and reason for death [if applicable])
- Follow-up of adverse events in case they were not yet recovered at the last FU visit.

Trial Protocol Version 12

Page 88 of 241

Proprietary confidential information. © 2022 Boehringer Ingelheim International GmbH or one or more of its affiliated companies. All rights reserved.

6.1.3.5 Patient completion

A patient has to be considered to have completed the trial if no further information is collected, i.e. in case any of the following applies:

- Completion of planned follow-up period (or planned observation period if applicable)
- Lost to follow-up
- Withdrawal to be followed-up
- Death

At the earliest of the above criteria, the Patient Completion (PC) information should be entered in the CRF.

6.1.3.6 End of whole trial

The trial will end when the last patient in both the phase Ib expansion and phase II has completed at least the last follow-up visit (as specified in Section 6.1.3.3) and an adequate number of overall survival events have been observed in phase II.

6.2 DETAILS OF TRIAL PROCEDURES AT SELECTED VISITS

The investigations and assessments will be performed as outlined in the Flow Chart and as per the descriptions listed below.

6.2.1 Screening period

Patients who failed screening may repeat the screening after discussion between investigator and sponsor providing that reasons for screening failure were reversible and have resolved.

Informed consent	Written informed consent must be obtained before any screening assessments are performed (with the exception of tumour scans as described in footnote 19 and 20 of the respective Flow Charts). Separate consent will be obtained, within the main consent form, for retaining blood and tissue samples for up to 15 years for future tests. Separate consent will be obtained, within the main consent form, for optional fresh biopsy for biomarker tumour analysis only in the phase II trial. See section 8.1.
Demographics and Medical History	Section 5.2.9.
Inclusion and exclusion criteria	See section 3.3.2 and 3.3.3 .

Doc. No.: c02304008-15

Proprietary confidential information. © 2022 Boehringer Ingelheim International GmbH or one or more of its affiliated companies. All rights reserved.

T	T
Physical examination, vital signs, height and body weight	Height recorded only at baseline visit and at no further visits. See section 5.2.8.
	Baseline conditions should be recorded at screening and up to start of treatment.
ECG 12-lead (triplicate)	See section 5.2.6.
ECHO/MUGA	See section 5.2.7.
ECOG performance score	As per Appendix 10.2.
Safety laboratory	Including haematology, biochemistry, coagulation parameters, urinalysis by dipstick.
	Fasting glucose and HbA1c only at screening and on Day 1 of every cycle. See section 5.2.5.
Prostate Serum Antigen (PSA)	Single blood sample collected for baseline PSA
Tumour assessment and bone scans/	To be performed within 28 days of day 1 of first treatment according to modified RECIST criteria version 1.1 (R09-0262) and prostate cancer clinical trials working group (PCWG2) criteria (R13-1642) as per section 5.1.2.1 .
Concomitant therapy	Collected from baseline and throughout study.
Compliance check of enzalutamide - Phase Ib expansion cohort only (for patients already taking enzalutamide throughout the screening period)	Review of diary card and compliance check of enzalutamide taken during screening period 7 days prior to C1 Day -1.

